However, these studies are limited in their assessment of pain and disability. Pain was often measured using Likert-scale questionnaires, as pain is an inherently subjective experience despite being physiologically determined [19]. Disability was assessed using more comprehensive questionnaires, but was not compared with objective measures [20]. This is despite objective measures of movement being correlated with disability scores [21]. A Cochrane review assessing the efficacy of heat therapies such as ThermaCare, indicated that there is only moderate support from current research, as effects

are transient and relatively small [22]. However, these reviewed studies may be limited due to their qualitative and subjective measurement of pain and disability [23]. A systematic review and meta-analysis further indicated that current heat therapy research is of "very-poor-quality" [24]. As such, validated, objective and quantitative data into muscle activity and movement is required, to provide insight into subjectively reported changes in pain and disability.

Objective assessment of the association between pain and movement, and capturing a detailed view of the person's movement, postures and activity levels is now possible due to the development of portable biofeedback sensors such as ViMove (dorsaVi Ltd). ViMove is wearable sensor technology, designed to precisely measure range of movement and static postures [25-27]. The device also measures low back muscle activity in real time through additional electromyography sensors. ViMove assessment of low back range of movement and posture has been shown to be highly correlated with 3D kinematic measurement [26]. Normative low back range of movement values have also been determined and are available for the adult population (normative data has FDA clearance, available upon request). The device also demonstrates high intra- and inter-rater reliability as a low back measurement tool [27]. Objective information and feedback is provided to the practitioner as a report evaluating a patient's movement and function/activity pre- and post- low back pain intervention. The wearable and portable nature of the device allows monitoring in non-clinical environments for up to 24 hours (i.e. during normal daily activities). ViMove devices have TGA approval and FDA 510K clearance for use in Australia and the USA respectively.

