### 11.2 Statistical Methods

An initial descriptive analysis will be completed on the baseline measures of movement to determine mean scores, ranges and standard deviations of each sample group. This analysis will be repeated at later time points. Wilcoxon Signed Ranked Tests will be completed to determine if participant movement significantly changes following an intervention: One each for Baseline and Intervention. A repeated measures ANOVA will then be completed on all post trial data for the 2 separate groups to determine movement changes in the post-trial period.

Bivariate correlational analyses through the Pearson product-moment coefficient, will be undertaken to determine if there is a relationship between movement and "pain on movement" using data collected at each time point. This potential relationship will be mapped to assess any temporal influences.

Similarly, correlational analyses will be conducted to determine if there is a relationship between daily activity and ODI scores, using data collected at each of the four total time points. This potential relationship will also be mapped over time to determine if there are any temporal effects following initial treatment.

All findings with a p-value < 0.05 will be deemed significant.

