### 13: STUDY OUTCOMES AND SIGNIFICANCE

# **13.1 Primary Endpoints**

- 1. Collection of movement and erector spinae muscle activity data in all participants.
- 2. Change over time in range of motion (ROM) in any one plane of movement compared to preintervention ROM.
- 3. A change over time in Flexion-Relaxation response in those subjects where abnormal EMG activity in flexion during baseline assessment is detected.
- 4. A change over time in maximum pain during movement score (1-10 as recorded during the inclinic ViMove assessment) for any one plane of movement.

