# **13.3 Significance**

This intervention study will provide information regarding changes in movement, flexibility, and pain following the use of ThermaCare HeatWraps in subjects who either suffer from low back pain, or are moderately or highly active. Moreover, it will assess any potential relationships between changes in pain, and responses to questionnaires as well as objectively measurable changes using ViMove systems.

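### Section 13.3 promises relationships between changes in pain and changes in movement, but section 11.2 plans only correlations of levels at each time point

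*Combined protocol and SAP*

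**What the plan says.** Section 11.2 (Statistical Methods) is the only place that specifies how movement is to be related to pain. It names the Pearson coefficient for movement against pain on movement, "using data collected at each time point. This potential relationship will be mapped to assess any temporal influences". A second correlation is handled the same way and asks "if there is a relationship between daily activity and ODI scores, using data collected at each of the four total time points". The Wilcoxon tests and the repeated-measures ANOVA in 11.2 concern movement alone.

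Section 13.3 (Significance) states a different target: "it will assess any potential relationships between changes in pain, and responses to questionnaires as well as objectively measurable changes using ViMove systems". The Background gives a related reason for collecting objective data, namely "to provide insight into subjectively reported changes in pain and disability". Two primary endpoints in section 13.1 are also changes: "Change over time in range of motion (ROM) in any one plane of movement compared to preintervention ROM" and "A change over time in maximum pain during movement score".

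No section describes a correlation of change scores, a repeated-measures correlation, or a model that separates within-person from between-person association.

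**The concern.** A correlation of levels at one visit asks whether people who move further report more or less pain than people who move less. That can reflect stable differences between people, such as age, build or habitual flexibility. Section 13.3 asks another question: whether the people whose movement changed are the people whose pain changed. Setting four per-visit correlations side by side over time does not answer it, because each one is still a comparison between people.

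If the wording means that all visits are pooled into one correlation, the two sources of variation are still mixed, and repeated measurements on one person are treated as independent.

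At stake is the interpretation of an exploratory result. Sections 8.2 and 11.1 describe a feasibility study meant to inform an RCT, and 11.2 calls any p-value below 0.05 significant. A level correlation read as a link between changes could pass a wrong idea to that trial, in either direction.

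**Working it through.** **The plan's own figures.** The only reproducible figure is recruitment: 40 / (1 - 0.20) = 50, which agrees with section 11.1. It has no bearing on this point. The plan gives no expected correlation, ICC, standard deviation or power for the correlations.

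**Inputs from the documents.** n = 20 per population (11.1); significance at 0.05 (11.2), taken as two-sided because the plan does not say; four live assessments per subject, at the start and end of Day 1 and of Day 2 (8.4 and Table 1).

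**Assumed inputs.** The ICC (the share of variance due to stable differences between people, set equal for movement and pain), the within-person correlation r_w and the between-person correlation r_b. The visit-specific parts are taken as independent across visits.

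**Formulas.** Each measurement is a stable person part plus a visit part. Then:

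- correlation of levels at one visit = ICC × r_b + (1 - ICC) × r_w
- correlation of change scores = r_w, because the person part cancels

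The two are equal for every ICC only when r_b = r_w.

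**Results for r_w = -0.6 and ICC = 0.8.**

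| r_b | Per-visit correlation | Change correlation |
|---|---|---|
| +0.3 | 0.24 - 0.12 = +0.12 | -0.60 |
| 0 | 0 - 0.12 = -0.12 | -0.60 |
| -0.3 | -0.24 - 0.12 = -0.36 | -0.60 |
| -0.6 | -0.48 - 0.12 = -0.60 | -0.60 |

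**Range over the ICC.** With r_w = -0.6 and r_b running from -0.5 to +0.5, the per-visit correlation runs:

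- ICC 0.5: -0.55 to -0.05
- ICC 0.7: -0.53 to +0.17
- ICC 0.8: -0.52 to +0.28
- ICC 0.9: -0.51 to +0.39

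**Simulation (20,000 runs, n = 20, ICC 0.8).**

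- r_w = -0.6, r_b = 0: the level analysis gave a significant negative correlation in 7% of runs, the change analysis in 84%.
- r_w = -0.6, r_b = +0.3: the level correlation was positive in 70% of runs.
- r_w = r_b = -0.6: both analyses averaged -0.59 and were significant in about 83 to 84% of runs.
- r_w = 0, r_b = -0.6: the level analysis was significant in 59% of runs although the changes were unrelated.

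**Precision at n = 20.** The Fisher z standard error is 1/√17 = 0.243. An observed correlation must exceed 0.44 in size to reach p < 0.05, and a true value of about 0.59 is needed for 80% power. An observed -0.12 has a 95% interval of about -0.53 to 0.34.

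**Measurement error in the changes.** If half the variance of each change score were error (an assumption), a true -0.6 would be observed as -0.6 × √(0.5 × 0.5) = -0.30. Power would then be about 25%, compared with about 82% for an observed -0.60.

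**The case against.** The strongest reply is that 11.2 asks only whether a relationship exists, which a per-visit correlation can answer. The promise about changes is one sentence in the Significance section, and no aim, hypothesis, objective or endpoint calls for a correlation of changes. The only correlation among the endpoints is the Low Back Pain Classifier score against ViMove scores. In a feasibility study, per-visit correlations are a legitimate description, and no decision rule rests on them. All of this stands and limits the weight of the point. It does not remove the mismatch between 13.3 and 11.2.

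The numbers are also open to challenge. A positive between-person correlation has no support in the documents. The Background says that movement measures correlate with disability scores but gives no sign. The within-person sign is itself uncertain: section 8.5.2 has subjects move as far as they can tolerate, so someone who improves may move further at the same pain. These objections stand, and the figures are therefore illustrations.

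A change analysis has limits too. The sport group has no pain entry criterion (7.1.2) and absence of pain is scored 0 (8.5.2), so many of its pain changes may be exactly zero. For activity against ODI, a start-of-day difference between Day 1 and Day 2 precedes the heat wrap, and section 8.4 plans no ODI at the end of Day 1.

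**Conclusion.** The point holds as a mismatch between stated purpose and planned analysis: 13.3 speaks of relationships between changes, and 11.2 relates levels only. The level correlations may understate, reverse or falsely suggest a link between changes, or may agree with it fully.

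A reader might infer that the planned analysis will hide or reverse the true link. The documents do not support that. They give no ICC and no correlations. With a within-person correlation of -0.6 and ICC 0.8, the sign reverses at a between-person correlation of +0.3, and nothing is lost at -0.6. Nor should one infer that change scores would recover the link with high power: the 84% in the simulation assumes no loss from measurement error.

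The point affects an exploratory analysis and leaves the primary endpoints untouched. It is worth acting on because the correction is cheap and uses assessments already planned.

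**What to change.** In section 11.2:

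- **Low back pain group.** Add a correlation of each subject's Visit 4 to Visit 5 change in ROM with the change in pain on movement in the same plane. Report the Visit 2 to Visit 3 changes in the same way as the no-heat comparison. Give confidence intervals and label the analysis exploratory, since several planes on two days mean several estimates.
- **Sport group.** Report it descriptively, and only where pain on movement is non-zero in enough subjects, with that number stated in advance.
- **Per-visit correlations, including activity against ODI.** Keep them as descriptive, and state that they are not read as relationships between changes.

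The cost is analysis wording only, with no new data or visits. The downside is that change scores are noisier than levels, so intervals will be wide: at n = 20, an observed -0.30 has a 95% interval of tanh(-0.310 ± 1.96 × 0.243), about -0.66 to +0.16.

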# 8.4 Methodology

The following tasks will be conducted on the recruitment day (Day 0) for all subjects, and will be recorded in each subject's respective source documents and case report forms (CRFs):

- 1. Assessment of eligibility against inclusion and exclusion criteria
- 2. An explanation of study procedures.
- 3. Provision and obtainment of written informed consent.
- 4. Obtainment of demographic information and medical history.
- 5. Booking of Day 1 and Day 2 (based on convenience).

The main study will be conducted over 2 consecutive days for each subject.

Participants will be asked to complete each of the following - 30 minutes prior to their appointment on Day 1; the Oswestry Disability Index (ODI), a Numeric Rating Scale for Pain (NRS Pain), the Roland Morris Disability Questionnaire, and a Low Back Pain Classifier.

Both subject groups will then have a "start interview" on their allocated baseline assessment day (Day 1). This will include fitting of the ViMove movement and EMG sensors, as well as a ViMove live "pain on movement" assessment. This session will take approximately 20-30 minutes. Whilst wearing the ViMove sensors, subjects will then leave the clinic and conduct normal daily activities for a predetermined monitoring period. No ThermaCare HeatWraps are worn on Day 1. This allows a baseline assessment and allows any placebo effects from the sensors to be discounted. At the end of the monitoring session, subjects will return to the clinic to have an "end-of-day" interview. Participants will complete a Patient Global Impression of Change scale (PGIC), a repeat NRS, and will have another live ViMove assessment. Movement sensors will then be removed, and the subject will be reimbursed for that day.

The intervention day (Day 2) will have the same procedure as Day 1 (baseline), with the only difference being the additional application of ThermaCare HeatWraps during the "start interview". ThermaCare will only be applied after the live assessment, so will not be worn at the same time as the EMG sensors. Subjects will continue to wear the HeatWrap and ViMove sensors during the 8-hour daily activity monitoring period, with the wrap and sensors being removed during the end-of-day interview, prior to the end-of-day live assessment. The subject will then be reimbursed for Day 2. A schedule of events can be seen in Table 1, and a summary of the procedure can be seen in Figure 1.

Table 1. Schedule of Events

[figure not shown]

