Tuble 1: Senedale of Events	Visit 1*	Visit 2*	Visit 3	Visit 4	Visit 5
		Baseline	Baseline	Intervention	
	(Day 0) Enrol-	Baseline Start	End of	Start	Intervention End of Day
		Interview		Interview	Interview
	ment		Day	interview	interview
		(within 3 weeks of	Interview		
		Visit 1)			
Eligibility	х				
Informed consent	х				
Demographics & Medical History	Х				
Enrolment and scheduling	Х				
Questionnaires		x		x	х
ViMove application		х		х	
ViMove in clinic assessment		х	Х	х	Х
ViMove monitoring assessment		х		х	
ViMove removal			Х		Х
ThermaCare application				х	
ThermaCare removal					Х
Adverse Events		х	Х	х	Х
Changes in medications		х		х	
Study Termination					х

\*Baseline may occur on the same day as Visit 1 (i.e. enrolment).

Subjects who withdraw from the study after providing informed consent are referred to as "dropouts" or premature withdrawals. The drop-out rate will be summarized. If the patient has provided a whole set of Day 1 data, this will be included in the study.

We expect 6-months will be required from first participant enrolment to the last participant visit. A further 3-months will be required for analysis and write-up.

Figure 1. Summarized Procedure

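### The activity-ODI correlation is planned at four time points although activity is recorded on two days, and section 8.4 and Table 1 do not settle whether ODI and RMDQ are collected after the wrap

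*Combined protocol and SAP*

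**What the plan says.** Section 11.2 correlates daily activity with ODI "using data collected at each of the four total time points", and the relationship is then to be "mapped over time to determine if there are any temporal effects following initial treatment".

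Table 1 in section 8.4 has separate rows for "ViMove in clinic assessment" (Visits 2, 3, 4 and 5) and "ViMove monitoring assessment" (Visits 2 and 4). The row "Questionnaires" is marked at Visits 2, 4 and 5 and names no instrument. "Study Termination" is at Visit 5.

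The prose of section 8.4 asks participants, "30 minutes prior to their appointment on Day 1", to complete "the Oswestry Disability Index (ODI), a Numeric Rating Scale for Pain (NRS Pain), the Roland Morris Disability Questionnaire, and a Low Back Pain Classifier". For the end of the day it lists only the Patient Global Impression of Change (PGIC), a second pain rating (NRS) and another live assessment. Day 2 is to run as Day 1 did apart from the wrap, which goes on after the start-of-day live assessment.

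Secondary endpoint 2 (section 13.2 and the summary) calls for change in ODI and RMDQ from before to after the wrap, limited to subjects scoring above 3 on the NRS. Objective 3 (section 3.3) concerns change in pain and disability after 8 hours of use.

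**The concern.** A correlation at a given time point needs both variables at that point. Four is not the number of occasions for either variable here, so the analyst would have to decide which ODI goes with which activity record, and for how many points, after the data exist.

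The second issue is potentially more costly. A site working from the prose would collect ODI and RMDQ only before heat is applied. Endpoint 2 and the disability part of Objective 3 would then have no post-treatment value, and a same-day score cannot be recovered once the two-day sequence is over. The study is meant to inform a later randomised trial, so the loss would carry into that planning.

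Third, the NRS condition in endpoint 2 does not say which reading it refers to, or whether it decides who completes the questionnaires or who is analysed.

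**Working it through.** This is a count of scheduled occasions; no power formula applies. Section 13.2 takes activity levels from ViMove monitoring, so daily activity here means the monitoring record.

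**Step 1: look for the plan's figure of 4.**

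| Measure | Source | Visits | Count |
|---|---|---|---|
| In-clinic ViMove | Table 1 | 2, 3, 4, 5 | 4 |
| NRS | 8.4 prose, Day 2 run as Day 1 | 2, 3, 4, 5 | 4 |
| Activity monitoring | Table 1 | 2, 4 | 2 |
| PGIC | 8.4 prose | 3, 5 | 2 |
| ODI/RMDQ, reading A | 8.4 prose, Day 1 only | 2 | 1 |
| ODI/RMDQ, reading B | 8.4 prose, repeated on Day 2 | 2, 4 | 2 |
| ODI/RMDQ, reading C | Table 1 row taken to include them | 2, 4, 5 | 3 |

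Four is reproduced by the in-clinic assessments and by the NRS. Neither is a variable in this correlation.

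**Step 2: match activity and ODI by day.** Visits 2 and 3 are Day 1; Visits 4 and 5 are Day 2. Activity exists for Days 1 and 2.

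- Reading A: ODI on Day 1 only, so 1 matched day; 4 − 1 = 3 short.
- Reading B: ODI on Days 1 and 2, so 2 matched days; 4 − 2 = 2 short.
- Reading C: ODI on Days 1 and 2, so 2 matched days; 4 − 2 = 2 short. Day 2 activity could be paired with the Visit 4 or the Visit 5 ODI. Counting both gives 1 + 2 = 3 pairings, still not four, and two of them share one activity record.

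**Step 3: count disability scores after the wrap.** ODI and RMDQ precede the start interview, and the wrap is applied during it.

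- Reading A: 0.
- Reading B: 0.
- Reading C: 1 (Visit 5).

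**Step 4: compare the questionnaire row with the prose.** At Visit 5 the mark could be met by PGIC and NRS alone, or could include ODI and RMDQ. At Visit 3 the row, as extracted, is blank, yet the prose requires PGIC and NRS there and section 8.5.4 also wants PGIC after Day 1. The row and the prose therefore disagree on at least one visit, and the row cannot settle what Visit 5 contains.

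**Step 5: count candidate NRS readings for endpoint 2.** Section 8.4 implies 4: three before the wrap (Visits 2, 3 and 4) and one after (Visit 5). The three-week average in the Group 1 inclusion criteria is a further candidate, so 4 + 1 = 5.

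**The case against.** The best reply concerns Visit 5. Section 8.4 itself refers the reader to Table 1, so a site following 8.4 also follows a table with a questionnaire mark at Visit 5. Section 4 lists ODI and RMDQ among the in-clinic questionnaires, and endpoint 2 expressly wants scores from both sides of the wrap. A row marked at Visit 5 but blank at Visit 3 even fits a row meaning the disability questionnaires. This stands to the extent that a reader who infers that the protocol omits post-wrap ODI and RMDQ goes further than the documents allow. It does not remove the conflict: no passage places either instrument at Visit 5, and the prose list for the end of the day leaves both out. Figure 1, which summarises the procedure, is not available here and might name them; the prose would still need to agree.

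A reader might also infer that the correlation cannot be run at all. That is too strong. A Day 1 and Day 2 analysis is possible wherever ODI is repeated on Day 2; what is wrong is the stated count and the missing pairing rule.

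Nor does the wording about effects after initial treatment clearly require activity recorded once the wrap is off. It can mean after application, and Day 2 monitoring follows application. That no activity is recorded after removal is true, but it is not shown to be a defect.

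Finally, this is a feasibility study, and the wrong count and the unnamed NRS reading are each small points. That is fair. The possible loss of post-wrap disability data is what gives the point weight.

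**Conclusion.** The point holds in three parts of unequal weight.

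- **Time points.** The stated four is wrong under every reading of the schedule: there are two activity records and one to three ODI occasions, giving one or two matched days. This rests only on daily activity meaning the monitoring record.
- **Post-wrap ODI and RMDQ.** The prose provides 0; Table 1 permits at most 1, at Visit 5, without saying so. This is an unreconciled conflict with a risk of unrecoverable data. Confidence is lower than for the count, because the table was read by a program and Figure 1 is missing.
- **NRS condition.** This is a minor gap in specification. A reader might infer that the condition biases endpoint 2. Selecting on a post-wrap score could remove improvers, and selecting on a high pre-wrap score in an uncontrolled design is open to regression to the mean. But the documents do not say which reading is meant and no size can be derived, so no bias is demonstrated.

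The primary endpoints are not touched. The changes are worth making, chiefly for the second part.

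**What to change.** 1. In section 11.2, restate the activity-ODI correlation for Day 1 and Day 2, and name the ODI reading paired with each day.
2. In section 8.4, state whether ODI and RMDQ are repeated on Day 2 and at which visits. Replace the single questionnaire row in Table 1 with one row per instrument, show PGIC and NRS at Visits 3 and 5, and make Figure 1 agree.
3. Choose one of two routes for endpoint 2 and Objective 3: (a) collect ODI and RMDQ at Visit 5 as well as before the wrap; or (b) reword both so that same-day change rests on NRS and PGIC.
4. In endpoint 2, name one pre-wrap NRS reading for the condition and say whether it governs administration or analysis.

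Items 1, 2 and 4 are wording edits, unless item 2 confirms a Day 2 ODI and RMDQ that sites had not planned. Route (b) adds no data collection but gives up the disability claim for the day of use. Route (a) keeps it, at the cost of two repeated questionnaires per subject (the ten ODI scales and the 24-point RMDQ) at a visit that already takes place.

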#### 1. In clinic assessments:

- a. Obtainment of demographic data and brief medical history.
- b. ViMove Assessment comprised of:
  - i. Assessment of Range of Movement (ROM) Flexion, Extension, Lateral Flexion, and rotation, standing and sitting positions, walking (40m speed test), sit-to-stand test (number of repetitions in 30 seconds and movement pattern, lift and carry task and squatting task).
  - ii. Simultaneous collection of muscle activity data using ViMove EMG sensors.
- c. Questionnaires:
  - i. Oswestry Disability Index (ODI)
  - ii. Roland Morris Disability Questionnaire
  - iii. Low Back Pain Classifier
  - iv. Numeric Scale for Pain (NRS-Pain)
  - v. Patient's Global Impression of Change Scale (PGIC)

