# 8.5.2 ViMove – Pain on movement

Pain on movement compares subjective responses of pain, with objective movement data from ViMove sensors. Assessment requires subjects to move within a maximum tolerable range. A numeric pain rating scale (see below) will be used during each movement, to obtain a value for the level of pain that each subject experiences. Consistent and standardized instructions are used, with the pain scores being recorded in the ViMove system. If no pain on movement is reported, a score of 0 will be documented.

(No Pain) 0 1 2 3 4 5 6 7 8 9 10 (Worst Pain)

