# 13.2 Secondary Endpoints

- 1. Capture changes in low back pain levels as assessed via a Numeric Rating Scale (NRS-Pain).
- 2. Capture self-reported changes in functional status pre- and post- ThermaCare application as measured by the Oswestry Disability Index (ODI) and Roland Morris Disability Questionnaire (RMDQ) if subjects scored >3 on the NRS.
- 3. Capture impression of change from subjects post ThermaCare application using the Patient Global Impression of Change Scale (PGIC).
- 4. Observe changes in activity levels as collected by ViMove monitoring.
- 5. Correlation of Low Back Pain Classifier (LBPC) Score to ViMove Scores for flexion and extension.

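### The blanket p < 0.05 rule in Section 11.2 covers an uncounted set of correlations, so the chance of a false significant relationship is at least about four times the nominal 5%

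*Combined protocol and SAP*

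**What the plan says.** Section 11.2 plans two sets of Pearson correlations. The first relates movement to pain on movement, "using data collected at each time point. This potential relationship will be mapped to assess any temporal influences". The second examines the "relationship between daily activity and ODI scores, using data collected at each of the four total time points". Section 13.2 lists a third as a secondary endpoint: "Correlation of Low Back Pain Classifier (LBPC) Score to ViMove Scores for flexion and extension". Section 11.2 then closes with "All findings with a p-value < 0.05 will be deemed significant".

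The plan does not say which movement or activity variables enter, whether the two groups are pooled, or how many coefficients will be computed. It gives these correlations no order of testing, no multiplicity adjustment and no exploratory label.

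Other sections indicate how large the set could be. Section 4 lists "Assessment of Range of Movement (ROM) Flexion, Extension, Lateral Flexion, and rotation" among the in-clinic measures. Section 8.5.2 says that a pain scale "will be used during each movement, to obtain a value for the level of pain that each subject experiences". Table 1 has in-clinic ViMove assessments at Visits 2, 3, 4 and 5. Section 11.1 sets two samples of 20.

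**The concern.** The closing sentence of 11.2 covers every finding, so each correlation is tested at 5% by itself and the error rate of the whole set is left uncontrolled. Because variables, time points and pooling are open, the set can also grow or be chosen after the data are seen.

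Section 13.3 makes relationships between pain, questionnaires and ViMove measures a stated output, and Sections 8.2 and 11.1 say that the study is meant to inform a randomised trial. Section 11.2 also intends to map the correlations over time. With four assessments, chance hits at one or two of them could be taken for a time pattern following treatment. At n = 20 any coefficient that passes will also look at least moderate in size.

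This differs from the multiplicity in the primary endpoints, which concerns change over time "for any one plane of movement" rather than correlation.

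**Working it through.** **The plan's own figure.** Section 11.1 recruits 50 to retain 40 at 20% attrition: 40 / (1 - 0.20) = 50, which reproduces. The plan states no power, number of tests or error rate for the correlations.

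**Inputs.** Threshold 0.05 per test (11.2; two-sided assumed, as sidedness is not stated). Four in-clinic assessments (Table 1). At least four movements (Section 4), each with its own pain score (8.5.2). Two groups of 20 (11.1). The number of tests m is not given, so three counts are shown:

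- A, barest reading: one movement x 4 time points + one activity measure x 4 time points, groups pooled: m = 4 + 4 = 8, n = 40.
- B, movement with pain in one sample: 4 movements x 4 assessments: m = 16, n = 20.
- C, as B in each group separately: m = 2 x 16 = 32.

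**Independent tests.** P(at least one p < 0.05 | no relationship) = 1 - 0.95^m, with 0.05m false positives expected.

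**Dependent tests.** Repeated visits and neighbouring movements are correlated, which lowers the chance. Null Pearson tests were simulated with normal data and assumed correlations of 0.3 to 0.7 between movements and 0.5 to 0.9 between visits. The two groups are different people, so C = 1 - (1 - p)^2, where p is the result for B: 1 - 0.655^2 = 0.571 and 1 - 0.454^2 = 0.794.

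| Count | m | Independent | With dependence | Expected false positives |
|---|---|---|---|---|
| A | 8 | 0.337 | 0.215-0.320 | 0.4 |
| B | 16 | 0.560 | 0.345-0.546 | 0.8 |
| C | 32 | 0.806 | 0.571-0.794 | 1.6 |

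The smallest entry is 0.215 / 0.05 = 4.3 times nominal, and the largest is 0.806 / 0.05 = 16.1 times. Under independence the chance passes one half at 14 tests (0.512).

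**Sensitivity.**

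- Stronger dependence: if all 16 test statistics in B are equally correlated at 0.8, the chance is 0.207 (4.1 times nominal). Two such groups give 1 - 0.793^2 = 0.371.
- Sport participants without pain: the share of zero scores is not given. Assuming 80% zeros, the sport group's rate is 34-54%, little changed. Assuming 95% zeros, it is about 19-29%, and C becomes 1 - 0.655 x 0.81 = 0.47 to 1 - 0.454 x 0.71 = 0.68. If all scores are 0, that group's coefficients are undefined and C reduces to B.
- Fewer ODI time points: with ODI at two time points, A has 4 + 2 = 6 tests, and 1 - 0.95^6 = 0.265 under independence. B and C contain no ODI tests.
- Additional tests: adding one activity measure at two time points to C gives 36 tests and 63-84%. The LBPC correlations are in none of these counts.

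**What a passing coefficient means.** At n = 20 the critical t on 18 degrees of freedom is 2.101, so |r| = 2.101 / sqrt(2.101^2 + 18) = 0.444. Its Fisher 95% CI is tanh(0.477 ± 1.96 / sqrt(17)) = 0.002 to 0.741. A result that just passes looks moderate yet is compatible with almost no relationship.

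**The case against.** The strongest reply is that this is a pilot. The summary, 8.2 and 11.1 call it a pilot or feasibility study, and the movement-pain and activity-ODI correlations are neither hypotheses (3.2) nor listed endpoints (13). Only the LBPC correlation is an endpoint, and it is secondary. How tightly such analyses should be controlled is partly a matter of judgement. That much stands, and it is a reason not to demand a formal adjustment. But the pilot label applies to the study as a whole and does not limit a sentence that covers all findings.

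A second reply is that the count is the reader's construction: 11.2 does not say one coefficient per movement, or one analysis per group. This also stands. A reader might infer that the study will probably report a false significant correlation, or that this is the expected result when no relationship exists. The documents do not support that. The 8-test reading stays well below one half, and a single 16-test sample mostly falls below it. Only separate testing of both groups per movement goes clearly above, and that depends on how many sport participants report pain, which entry to that group does not require.

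Third, the activity-ODI set may be smaller than written. Monitoring runs on two days, and the end-of-day text in 8.4 names only the global impression of change and a repeat pain rating.

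Finally, a reader might infer that a chance correlation will decide the later trial's movement, time point or measure. No section says so. It is a risk, not a plan.

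**Conclusion.** The point holds as a defect in the significance rule, of moderate importance. Followed as written, 11.2 declares correlations significant with a chance of at least one false finding of about 22-34% (8 pooled tests), 35-56% (16 tests in one sample) or 57-81% (32 tests across both groups), against a nominal 5%.

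The spread reflects what the plan leaves open: the number of coefficients, pooling, the dependence between tests and how many sport participants report pain. The dependence values are assumptions. Extreme dependence, or nearly all sport participants scoring 0, would lower the 16- and 32-test figures as shown, though not to near 5%. The conclusion is that the error rate is several times nominal and undeclared, not that a false finding is more likely than not.

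**What to change.** Add one sentence to 11.2: *The correlational analyses (movement with pain on movement, daily activity with ODI, LBPC with ViMove scores) are exploratory; each coefficient will be reported with a 95% CI together with the number computed, and the p < 0.05 rule does not apply to them.*

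Keep the change to the correlations. Restricting the rule to the primary endpoints would also remove it from secondary endpoints that are not correlations (pain rating, disability scores, impression of change, activity). It would also seem to endorse unadjusted testing of primary endpoints met in any single plane. Those should be dealt with separately.

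Reconcile the four time points stated for ODI in 11.2 with the text of 8.4 and with Table 1, which as extracted marks questionnaires at Visits 2, 4 and 5 without saying which ones.

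The cost is that individual correlations can no longer be called significant. No data, visits or participants change.
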